9.3.7. Other Analyses

On treatment analysis of efficacy endpoints

As sensitivity analyses, the primary and key secondary objectives will be tested using the OT population during the on-treatment period.

Pre-Specified Subgroups of Interest

Subgroup analyses for the primary outcome will be performed to assess whether the therapeutic effect is consistent across all patients, or whether it varies according to specific patient

characteristics. These analyses will focus on whether the relative therapeutic effect differs according to the following baseline variables:

- Age (<70 years vs. ≥70 years)
- Sex (male vs. female)
- Race (white vs. racial minorities)
- AF type (paroxysmal vs. persistent, or long-standing persistent)
- Left atrial dimension (<50 mm versus ≥50 mm)
- AF duration (<30 days versus ≥30 days)
- Structural heart disease (present vs. absent)
- Hypertension (present vs. absent)
- Chronic kidney disease (estimated eGFR ≤60 vs. >60 ml/min)
- CHA₂DS₂-VASc score (0-1 vs. ≥2 excluding sex)
- Sleep Apnea (present vs. absent)
- BMI (<30 vs. ≥30)
- Heart failure vs no heart failure
- Left ventricular ejection fraction (LVEF) (41-55 vs. >55)
- Recent hospitalization for AF vs None

Cox proportional hazards regression modeling will be used to assess whether treatment effect is heterogeneous across pre-specified subgroups. For each subgroup analysis, the Cox proportional hazards model will be fit for time to first event including the subgroup as a stratification factor, and the treatment group and interaction between treatment and subgroup as covariates. The treatment effect within each subgroup level will be presented as a hazard ratio (dronedaron on top of usual care vs. usual care) and a 95% CI. Heterogeneity will be assessed by presenting the interaction P-value, using a two-sided test.

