5.1. Inclusion Criteria

Participants are eligible to be included in the study if the following apply:

1. Age 21 years or older.
2. First-detected atrial fibrillation (defined as atrial fibrillation diagnosed in the previous 120 days)
3. Electrocardiographic documentation of atrial fibrillation. §
4. Estimated life expectancy of at least 1 year
5. Patient or legal authorized representative capable of giving signed informed consent, which includes compliance with the requirements and restrictions listed in the informed consent form (ICF) and in this protocol.

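### Section 9.3.7 tests effect modification by seven numeric or score variables only through one cut each; a prespecified interaction on the underlying value should be added beside the categorical test

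*Protocol*

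**What the plan says.** Section 9.3.7 of the Protocol lists fifteen baseline subgroups for the primary outcome. The declared purpose is to see whether the treatment effect is the same for all patients or differs with their characteristics.

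Seven of the fifteen rest on a number or a score, and each is given one cut:

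- age: "Age (<70 years vs. ≥70 years"
- left atrial dimension: "Left atrial dimension (<50 mm versus ≥50 mm"
- AF duration: "AF duration (<30 days versus ≥30 days"
- kidney function: "Chronic kidney disease (estimated eGFR ≤60 vs. >60 ml/min"
- ejection fraction: "Left ventricular ejection fraction (LVEF) (41-55 vs. >55"
- BMI: cut at 30
- CHA2DS2-VASc without the sex point: 0–1 against 2 or more

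The model is fixed as well. It is a Cox model "including the subgroup as a stratification factor, and the treatment group and interaction between treatment and subgroup as covariates", and "Heterogeneity will be assessed by presenting the interaction P-value, using a two-sided test". The section describes no interaction on the underlying value and states no power for any interaction.

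Section 5.1 sets the range of AF duration at entry: "First-detected atrial fibrillation (defined as atrial fibrillation diagnosed in the previous 120 days".

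**The concern.** Cutting a numeric variable before testing its interaction with treatment treats everyone on the same side of the cut as alike. If the effect changes gradually, that discards information and makes the answer depend on where the cut was placed.

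AF duration is the clearest case. The trial's question is early treatment. Section 4.2 cites an ATHENA subgroup analysis suggesting better results with shorter AF duration, and Section 9.5 takes the assumed hazard ratio of 0.79 from ATHENA patients with less than 3 months of AF history. Yet within the 120-day window the planned test treats day 30 and day 120 as identical, and day 29 and day 30 as different.

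Interaction tests in a trial of this size are weak to begin with. A weak test that comes out non-significant can be read as evidence of a consistent effect, which is the question this section sets out to answer.

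**Working it through.** **The plan's own figure.** Section 9.5 gives 733 events and a power of 0.89 at a hazard ratio of 0.79, two-sided alpha 0.05. By Schoenfeld's formula, power = Φ(√733/2 × |ln 0.79| − 1.96) = Φ(13.54 × 0.2357 − 1.96) = Φ(1.23) = 0.89. The figure is reproduced. It concerns the main effect only.

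**How weak a binary interaction already is.** With 733 events and subgroups holding shares p and 1−p of them, the standard error of the log ratio of hazard ratios is about √(4/(733p) + 4/(733(1−p))).

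- 50/50: √(16/733) = 0.148. For 80% power the ratio must be exp(2.802 × 0.148) ≈ 1.5.
- 90/10: √(4/659.7 + 4/73.3) = 0.246. The ratio must be exp(2.802 × 0.246) ≈ 2.0.

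**Information kept by one cut when the true interaction is linear.** This is the squared correlation between the variable and its two-level version:

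- normal variable: φ(z)²/(p(1−p)), where z is the cut in standard units
- uniform variable: 3p(1−p)

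For an interaction with 80% power on the numeric scale, power after the cut is Φ(2.802 × √kept − 1.96).

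| Assumed shape and split | Kept | Lost | Power after the cut |
|---|---|---|---|
| Normal, 50/50 | 0.637 | 36% | 61% |
| Normal, 70/30 | 0.576 | 42% | 57% |
| Normal, 85/15 | 0.43 | 57% | 45% |
| Uniform, 50/50 | 0.75 | 25% | 68% |
| Uniform 0–120 days, cut at 30 (p = 0.25) | 0.5625 | 44% | 56% |

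Worked line for the normal median split: 0.3989²/0.25 = 0.637; 2.802 × √0.637 − 1.96 = 0.276; Φ(0.276) = 0.61.

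**Range over plausible distributions, all assumed, with a linear interaction.** Loss is 37–44% for age, about 38% for BMI, 42–51% for eGFR, 35–51% for LVEF, 25–56% for CHA2DS2-VASc and 51–71% for left atrial dimension, where few patients would lie above the cut.

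**AF duration depends most on the assumption.** Exponential-like or uniform durations lose 33–53%. Two clusters lose 10–33%. One such case is half the patients uniform over days 0–7 and half over days 45–120. The means are 3.5 and 82.5, so the variance between clusters is (79/2)² = 1560. The average variance within them is (49/12 + 5625/12)/2 = 236. The cut at 30 separates the clusters exactly, so it keeps 1560/(1560 + 236) = 0.87 and loses 13%.

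**Check by simulation.** Cox models were fitted to 3000 simulated patients (hazard ratio 0.79, 150 replicates per scenario), comparing the stratified two-level model of Section 9.3.7 with a numeric interaction. The information ratio, two-level to numeric, was 0.63 for a normal variable and 0.72 for a uniform one at the median split, close to the formulas. When the truth was a step exactly at the cut, the ratio was 1.59 in favour of the two-level model.

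**Step away from the cut (normal variable, cut at the median).** A step 0.25 SD away costs the two-level test 33% and the linear term 38%. At 0.5 SD the order reverses: 55% against 42%.

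**The case against.** The strongest reply has five parts.

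1. **The loss is conditional.** A reader might infer that every one of these tests throws away at least a quarter of its information. The documents do not support that. They give neither a distribution nor a shape for any interaction. A step at the cut loses nothing, and the linear term would then lose 36%. Sections 1.2 and 8 allow enrolment during an acute encounter or at a later outpatient visit, so clustered AF durations with a loss near 10% are quite possible. This part stands.

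2. **The cuts have a benefit.** A reader might also infer that the categorical test has nothing in its favour. In fact its P-value belongs to the same contrast as the hazard ratios displayed, it does not assume linearity, and its cuts are fixed in advance. This stands, and is why the categorical test should be kept.

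3. **Nothing decisive depends on it.** Section 9.1.1 confines formal testing to the primary objective and the win ratio. This stands and limits the weight of the point.

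4. **It belongs to the SAP.** Section 9 calls itself a summary, and the SAP, not at hand, may add a numeric analysis. This stands only in part. Section 9.3.4 defers the tertiary analyses to the SAP, whereas Section 9.3.7 specifies both the cuts and the model.

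5. **The numbers may not all be recorded.** Section 1.2 names ejection fraction data but not left atrial dimension, and the protocol requires no tests of its own. This stands, so the fix applies where the value exists. Section 9.3.5 already plans to use time since AF diagnosis in handling missing quality-of-life data, so that variable should be available.

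**Conclusion.** The point holds as a modest, conditional one. The only heterogeneity test that the protocol describes for these seven variables uses one cut each. Under a roughly linear interaction, this typically costs about 25–50% of the information for most of them, and possibly more for left atrial dimension. An interaction with 80% power on the numeric scale would then have about 68% power at a 25% loss, 61% at 36% and 51% at 50%.

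The conclusion rests on two assumptions that the protocol neither supplies nor excludes: the shape of the interaction and the distributions at baseline. No section argues for a threshold at any of the listed cuts, so a gradual change is at least as plausible as a step.

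The planned test is not invalid. The point does not reach the primary analysis, the type I error, the sample size or the stated 89% power.

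**What to change.** Keep the listed categories, their hazard ratios and the categorical interaction P-value. Add to Section 9.3.7, or to the SAP before unblinded data are seen, a sentence to this effect:

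*For age, left atrial dimension, AF duration, eGFR, CHA2DS2-VASc, BMI and LVEF, where the numeric value is recorded, a Cox model with treatment, the numeric baseline value and their product will also be fitted and a two-sided interaction P-value reported; a restricted cubic spline will be used to check the shape.*

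Name AF duration as the first of these. Fix the linear term as the test and use the spline only as a check. An effect with 80% power on a correct one-degree-of-freedom linear test has about 71% on two degrees of freedom and 64% on three, before any gain from a better fit.

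The cost is a little programming and up to seven more supportive P-values. The added test carries a linearity assumption, and it may disagree with the categorical result; if so, both should be shown. No new data are needed where the number is already captured.

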9.4. Data Safety & Monitoring Board & Interim Analysis

There will be a Data and Safety Monitoring Board (DSMB) in this pragmatic clinical trial. The DSMB will be an independent group of experts that advises the principal investigator, steering committee, and study investigators. The DSMB will consist of one statistician and two clinicians with expertise in clinical trials and in the management of AF. The members of the DSMB will serve in an individual capacity and provide their expertise and recommendations.

The DSMB will meet approximately every 6 months to monitor the recruitment and conduct of trial, data quality and timeliness, the distribution of therapies within the study groups, the occurrence of safety and other events selected to their discretion during the course of the trial. The DSMB chair will receive a quarterly report between two regular meetings.

Since the event rate of the primary outcome is closely associated with the statistical study power, a blinded sample size and power analysis based on the overall event rate will be included in the regular DSMB report. Recommendations for the sample size adjustment by DSMB will be made before the interim analysis based on trying to maintain ≥ 85% power for the primary outcome and allow to increase as much as 35% but no reduction.

If a clinically significant imbalance in efficacy or safety events between the groups is observed at any time, the DSMB Chair may request an unblinded analysis. Similarly, if the DSMB identifies any other concerns, the Chair can call a separate meeting. A DSMB charter providing operating procedures and responsibilities will be discussed, drafted, and implemented by the DSMB and an unblinded statistician.

In addition to these routine safety reviews, an interim analysis for efficacy and futility of the primary objective is planned at approximately 50% of total information, i.e. when 50% of the expected total number of events (approximately 733 events, see **Table 4** below) are collected. The Lan-DeMets spending function similar to the O'Brien-Fleming boundaries will be used to monitor the efficacy of the primary outcome as a guide for the DSMB. See **Table 4** for the details of these procedures. This spending function is conservative in that priority is given to preserving power for the final analysis with the use of stringent stopping rules early in the study. For futility, conditional power will be calculated under originally hypothesized hazard ratio, the null hypothesis and the observed trend at the interim analysis and will be compared with 10%. The futility stopping rules will be considered non-binding by the DSMB in their review of interim data.

If the primary endpoint is declared to be statistically significant in the favorable direction at a one-sided alpha level of 0.025, WIN ratio as the first key secondary endpoint will be tested according to an OBF-like boundary. See **Table 4** for the details of these procedures.

Table 4. Significance level for the primary endpoint and WIN ratio

	At the interim analysis at 50%	At the final analysis	One-sided nominal significance level
One-sided significance level for the primary hypothesis	0.0153	0.0245	0.025
One-sided significance level for WIN ratio if the primary endpoint is declared significant	0.0153	0.0245	0.025

The Steering Committee will approve the timing of all interim analyses proposed by the DSMB. If the DSMB determines there is absence of futility, acceptable safety, and pre-trial assumptions regarding the endpoint event rate and other factors are correct, the trial will continue as planned.

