9.1.1. Multiplicity Adjustment

Formal statistical hypothesis testing will be restricted to the primary objective and the WIN ratio (the first secondary objective). Type I error (one-sided $\alpha=0.025$) will be controlled for these objectives using the gatekeeping testing strategy adapted from Maurer & Bretz (2013),⁶³ accounting for one unblinded interim analysis. The details of multiplicity adjustment are described in Section 9.4 below.

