9.3. Statistical Analyses

9.3.1. General Considerations

- A detailed Statistical Analysis Plan (SAP) will be developed and contained in a separate document. Study population details including the number randomized to each treatment arm, the number completing the study, and lost to follow-up will be described. Baseline participant characteristics will be summarized as means, standard deviations, medians, and/or 25th, 75th percentiles for continuous variables, and as counts and percentages for categorical variables. Unless otherwise stated, tests of hypotheses about the efficacy of dronedarone will be one-sided ($\alpha=0.025$) and effect estimates will be presented with nominal 95% confidence intervals (CI).

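### Table 4's interim level of 0.0153 is ten times what the named spending function gives (0.00153); applied as printed, the boundaries have a one-sided type I error of about 0.034, not 0.025

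*Protocol*

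**What the plan says.** Section 9.1.1 of the protocol sets the overall error: "Type I error (one-sided $\alpha=0.025$) will be controlled for these objectives using the gatekeeping testing strategy", and adds that this is done "accounting for one unblinded interim analysis". Section 9.4 places that look at roughly 50% of the information and names the method: "The Lan-DeMets spending function similar to the O'Brien-Fleming boundaries will be used to monitor the efficacy of the primary outcome". It then describes the character of the rule: "This spending function is conservative in that priority is given to preserving power for the final analysis with the use of stringent stopping rules". The futility rule is non-binding.

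For the numbers, section 9.4 sends the reader to Table 4 twice, once for the primary endpoint and once for the WIN ratio. The primary row is "One-sided significance level for the primary hypothesis 0.0153 0.0245 0.025", where the three figures are the interim, final and overall levels. The row labelled "One-sided significance level for WIN ratio if the primary endpoint is declared significant" holds the same three figures.

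The timing of the look is given as "when 50% of the expected total number of events (approximately 733 events", with a pointer to Table 4. The total of 733 events is in fact in Table 5 of section 9.5, in the column for a hazard ratio of 0.79.

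**The concern.** O'Brien-Fleming-type spending uses very little alpha at the halfway point. That is why the final level stays close to the full 0.025. An interim level of 0.0153 is more than half of the whole allowance, so it cannot sit beside a final level of 0.0245 unless the overall error exceeds 0.025.

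Table 4 is the only place in the protocol where numerical efficacy boundaries appear. An interim one-sided p-value between 0.00153 and 0.0153 would cross the printed boundary but not the one implied by the named method. The data monitoring board would then hold two conflicting rules at the moment of a stop-or-continue decision, and an early stop for efficacy cannot be undone.

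**Working it through.** **Inputs.** Overall one-sided alpha 0.025 (sections 9.1.1 and 9.3.1). Lan-DeMets O'Brien-Fleming-type spending with one look at information fraction t = 0.5 (section 9.4). Printed levels 0.0153 and 0.0245 (Table 4). 733 events and power 0.89 at a hazard ratio of 0.79 (Table 5). Allocation is 1:1. The futility rule is non-binding, so it earns no credit in the type I error.

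**Step 1: the boundary that the stated rule implies.** The spend at the interim is 2 × [1 − Φ(z/√t)] with z = Φ⁻¹(1 − 0.025/2) = 2.2414. At t = 0.5 this is 2 × [1 − Φ(2.2414/0.7071)] = 2 × [1 − Φ(3.170)] = 0.001525, a critical value of 2.963. The final level then solves P(Z1 > 2.963 or Z2 > c) = 0.025, where (Z1, Z2) is bivariate normal with correlation √0.5. The result is c = 1.969, a level of 0.02450. The printed final level is reproduced. The printed interim level is not: 0.0153/0.001525 = 10.03.

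**Step 2: overall one-sided type I error**, computed as 1 − P(Z1 < c1, Z2 < c2) under the null:

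| Interim level | Final level | Overall error |
|---|---|---|
| 0.00153 | 0.0245 | 0.0250 |
| 0.0153 | 0.0245 (as printed) | 0.0337 |
| 0.0153 | 0.0141 (solved to hold 0.025) | 0.0250 |

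A simulation of four million draws gave 0.0339 for the printed pair. Relative inflation is 0.0337/0.025 = 1.35.

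**Step 3: could another rule explain 0.0153 with 0.0245?**

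| Rule | Interim | Final |
|---|---|---|
| Classic O'Brien-Fleming | 0.0026 | 0.0240 |
| Pocock | 0.0147 | 0.0147 |
| Lan-DeMets, Pocock type | 0.0155 | 0.0139 |
| O'Brien-Fleming-type spending at one-sided 0.05 | 0.0056 | 0.0482 |

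None gives the printed pair. If 0.0153 is read as two-sided (0.00765 one-sided) beside a one-sided 0.0245, the overall error is 0.0284. If both are read as two-sided, it is 0.0173. The named function reaches a cumulative spend of 0.0153 only at about 85% of the information.

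**Step 4: what the printed level would do at the look.** Half of 733 is 366.5 events. With standard error 2/√d for the log hazard ratio, the boundary is exp(−2z/√366.5):

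- 0.0153 (z = 2.162): hazard ratio 0.798
- 0.00153 (z = 2.962): hazard ratio 0.734

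For a true hazard ratio of 0.79, the expected final statistic is −ln(0.79) × √733/2 = 3.191, and at half information it is 3.191 × √0.5 = 2.256. The chance of crossing at the interim is Φ(2.256 − 2.162) = 0.54 with the printed level and Φ(2.256 − 2.963) = 0.24 with 0.00153.

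**Step 5: power.** At a hazard ratio of 0.79 and 733 events, the pair 0.00153 / 0.0245 gives 0.890, matching the stated 0.89. The printed pair gives 0.897. This agrees with 0.00153 but is weak evidence by itself, because a fixed design with no interim also gives 0.891. The agreement of the final level in Step 1 is the stronger evidence.

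**The case against.** The strongest reply is that the governing rule is the spending function, not the table. A statistician who applies the named function obtains 0.00153 and holds 0.025. The boundaries are described as a guide for the board, and the SAP and board charter, not available here, may print the right figure. This stands to the extent that the inflation to 0.034 is conditional on the printed levels being used. It does not remove the fault: the protocol refers the reader to Table 4 for the procedure, and the table contradicts the method named beside it.

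Three narrower points are fair:

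- The 0.0337 figure is for the primary endpoint. The WIN ratio row has the same misprint, but that test is gated on the primary endpoint and its error rate was not calculated.
- A one-sided 0.0153 is still stricter than 0.025. The complaint is that it is far too lenient for the rule named, not that it is lax in every sense.
- The parenthesis with 733 events can be read correctly as the total to which the 50% applies. The definite slip there is the reference to Table 4 instead of Table 5; beyond that, the wording is only ambiguous.

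A table broken in reading the PDF is an unlikely explanation, since both rows show the same figure.

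**Conclusion.** The concern holds. The interim level in both rows of Table 4 is wrong by a factor of ten. The matching digits (153) and the correct final level point to a misplaced decimal. The printed primary boundaries, taken literally, give a one-sided type I error of 0.0337 against the 0.025 that section 9.1.1 says is controlled. They would also allow a stop at an observed hazard ratio of 0.798, a smaller effect than the design value of 0.79, under a rule that the text presents as stringent early on.

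These figures assume a look at exactly half of the information and the usual independent-increments normal approximation. The hazard-ratio thresholds and crossing probabilities also assume 733 total events, 1:1 allocation and proportional hazards. The design itself is sound once the figure is corrected. The correction must be in place before the interim analysis.

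**What to change.** In Table 4, replace 0.0153 with 0.00153 in both the primary and the WIN ratio rows and keep 0.0245. In the sentence on timing, write that the look takes place at about 367 of 733 expected events and refer to Table 5. Check that the SAP and the board charter carry the corrected value.

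Optionally, add that the levels will be recomputed from the spending function at the information fraction actually observed. This is inherent in the Lan-DeMets method, but stating it makes clear that the table is illustrative for a look at exactly 50%.

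The cost is one corrected table and one sentence in a protocol amendment. No patients are added, and the power at a hazard ratio of 0.79 stays at 0.89.

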9.5. Sample Size Determination

- With a planned accrual time of 1.5 years, a fixed follow-up period of 1 year, an assumed lost to follow up of 20% before 12 months (assuming exponential distribution for time-to-censoring), a two-sample log-rank test with two-sided alpha of 0.05, a cumulative incidence function (CIF) of 30% at 12 months in the usual care arm, an assumed hazard ratio of 0.79, one interim analysis using the Lan-DeMets spending function similar to the O'Brien-Fleming boundaries, a planned sample size of 3000 patients (1500 patient per arm) provides approximately 89% study power as shown in the following table:

**Table 5. Study power and number of events with 3000 patients
Estimated by Markov chain Monte Carlo simulations with 10,000 iterations**

Hazard Ratio (Dronedarone vs. Usual care)	0.78	0.79	0.80
Nominal Power	0.92	0.89	0.86
Total number of events	730	733	737

[figure not shown]
- The study will be conducted at sites participating in the GWTG-AFIB Registry. Some sites will be centers that are established GWTG-AFIB sites and others will be recruited to participate in GWTG-AFIB for the purpose of this study. We will attempt to achieve a total of up to 200 sites. There have been more than 40,000 patients included in the GWTG-AFIB Registry. For the purpose of this pragmatic trial, patients will be approached at the time of their first-detected AF episode. Preliminary query of the GWTG-AFIB database suggests that greater than 1400 patients were enrolled each year in GWTG with new-onset AF and no heart failure. Using the Jan 2020 GWTG-AFIB data harvest, there were a total of 8,192 patients meeting the inclusion/exclusion criteria (see Table 6). As we plan to include sites beyond GWTG-AFIB sites, we plan to enrol 3000 patients in 18 months.

Table 6. Distribution of Admissions for GWTG-AFIB Registry Patients

Admission Year	Frequency (patients)	Percent	Cumulative Frequency (patients)	Cumulative Percent
2013	65	0.79%	65	0.79%
2014	390	4.76%	455	5.55%
2015	1229	15.00%	1684	20.56%
2016	1429	17.44%	3113	38.00%
2017	1750	21.36%	4863	59.36%
2018	1871	22.84%	6734	82.20%
2019	1458	17.80%	8192	100.00%

In the ATHENA trial a post-hoc analysis was conducted that analyzed events according to the duration of AF history.²⁶ Using event rates in the placebo and dronedarone arms among patients with a duration of AF history <3 months (45% of the ATHENA study cohort), the expected hazard ratio for dronedarone vs. placebo was ~0.79 for the primary endpoint of CV hospitalization or death evaluated through 12 months of follow-up. The event accumulation in placebo arm through 12 months in the ATHENA trial was CIF% of approximately 10%, 20%, 25%, and 30% at 3, 6, 9, and 12 months, respectively, as shown in **Figure 1**.²⁶ The estimated sample size by various statistical power and hazard ratio are shown in **Table 7**. To account for one interim analysis using the Lan-DeMets spending function similar to the O'Brien-Fleming boundaries, the estimated sample size should be inflated by 1.01.⁶⁶ Therefore, the study will enroll approximately 3000 patients.

Figure 1. Event accumulation in placebo arm through 12 months in the ATHENA trial

No. at Risk							
Placebo	2327	1858	1625	1072	385	3	
Dronedarone	2301	1963	1776	1177	403	2	

Table 7. Total sample size estimated with 20% attrition by 12 months, two-sided log-rank test, alpha=0.05, placebo CIF curve like ATHENA (30% with event by 12 months)

Nominal Power	Hazard Ratio (Dronedarone vs. Placebo)					
	0.75	0.76	0.77	0.78	0.79	0.80
0.85	1794	1960	2148	2364	2612	2898
0.86	1848	2018	2212	2434	2688	2984
0.87	1904	2080	2280	2508	2770	3074
0.88	1964	2146	2352	2588	2858	3172
0.89	2030	2216	2430	2674	2954	3278
0.90	2100	2294	2514	2766	3056	3392

10. Supporting Documentation and Operational Considerations

